APPENDIX I

ACUTE GRAFT VS. HOST DISEASE GRADING SCALE

Acute GVHD Staging:

Stage	Skin	Liver	Intestine
0	No rash	Bilirubin \leq 2 mg/dl	< 500 mL diarrhea per day
1	Maculopapular rash <25% of body surface	Bilirubin 2-3 mg/dl	>500-1000 mL diarrhea per day or persistent nausea/vomiting/anorexia
2	Maculopapular rash 25-50% of body surface	Bilirubin 3.1-6 mg/dl	>1000 -1500 mL diarrhea per day
3	Maculopapular rash >50% body surface area or Generalized erythroderma	Bilirubin 6.1-15 mg/dl	>1500 mL diarrhea per day
4	Generalized erythroderma with bullous formation and desquamation	Bilirubin >15 mg/dl	> 2000 mL diarrhea per day or severe abdominal pain +/-ileus

Acute GVHD Grading:

Grade	Skin	Liver	GI
I	Stage 1-2	0	0
II	Stage 3 or	Stage 1 or	Stage 1
III	----	Stage 2-3	Stage 2-4
IV	Stage 4	Stage 4	NA

Conversion chart for staging the volume of Diarrhea in Pediatric Patients: (Source adapted from the modified keystone criteria GVHD reporting form) and the pediatric GUT GVHD staging is based on the CIBMTR/ CTN technical manual of practice version 2 (Sep, 2005).

STAGE

- 0
- 1
- 2
- 3
- 4

STOOL VOLUME

- none or diarrhea < 280 ml/m²/day
- 280-555 ml/m²/day
- 556-833 ml/m²/day
- > 833 ml/m²/day
- severe abdominal pain, w/ or w/out ilius

APPENDIX II

CHRONIC GVHD SCORING: using NIH consensus criteria

	Score 0	Score 1	Score 2	Score 3
Performance Score: 

 KPS ECOG LPS	 Asymptomatic and fully active (ECOG 0; KPS or LPS 100%)	 Symptomatic, fully ambulatory, restricted only in physically strenuous activity (ECOG 1; KPS or LPS 80-90%)	 Symptomatic, ambulatory, capable of self-care, > 50% of waking hours out of bed (ECOG 2; KPS or LPS 60-70%)	 Symptomatic, limited self-care, > 50% of waking hours in bed (ECOG 3-4; KPS or LPS < 60%)
SKIN Clinical Features:  Maculopapular rash  Lichen planus-like features  Papulosquamous lesions or ichthyosis  Hyperpigmentation  Hypopigmentation  Keratosis pilaris  Erythema  Erythroderma  Poikiloderma  Pruritus  Sclerotic features  Hair involvement  Nail involvement % BSA involved: 

	 No symptoms	 < 18% BSA with disease signs but NO sclerotic features	 19-50% BSA OR involvement with superficial sclerotic features "not hidebound" (able to pinch)	 > 50% BSA OR deep sclerotic features "hidebound" (unable to pinch) OR impaired mobility, ulceration or severe pruritus
MOUTH	 No symptoms	 Mild symptoms with disease signs but not limiting oral intake significantly	 Moderate symptoms with disease signs WITH partial limitation of oral intake	 Severe symptoms with disease signs on examination WITH major limitation of oral intake
EYES Mean tear test (mm):  > 10  6-10  < 5  Not done	 No symptoms	 Mild dry eye symptoms not affecting ADL (requiring eye-drops < 3 x/day) OR asymptomatic signs of keratoconjunctivitis sicca	 Moderate dry eye symptoms partially affecting ADL (requiring eye-drops > 3 x/day or punctal plugs), WITHOUT vision impairment	 Severe dry eye symptoms significantly affecting ADL (special eyewear to relieve pain) OR unable to work because of ocular symptoms OR loss of vision caused by keratoconjunctivitis sicca
GI TRACT	 No symptoms	 Symptoms such as	 Symptoms associated with	 Symptoms associated with significant weight

		dysphagia, anorexia, nausea, vomiting, abdominal pain or diarrhea without significant weight loss (< 5%)	mild to moderated weight loss (5-15%)	loss >15%, requires nutritional supplement for most calorie needs OR esophageal dilation
LIVER AST ____ ALT ____ AP ____ Tbili	 Normal LFT	 Elevated Bilirubin, AP, AST or ALT < 2x ULN	 Bilirubin > 3 mg/dl or bilirubin, enzymes 2-5x ULN	 Bilirubin or enzymes > 5x ULN
LUNGS FEV1  DLCO 	 No symptoms  FEV1 > 80% OR LFS =2	 Mild symptoms (SOB climbing one flight of stairs)  FEV1 60-79% OR LFS 3-5	 Moderate symptoms (SOB after walking on flat ground)  FEV1 40-59% OR LFS 6-9	 Severe symptoms (SOB at rest; requiring O2)  FEV1 40-59% OR LFS 6-9
JOINTS AND FASCIA	 No symptoms	 Mild tightness of arms or legs, normal or mild decreased range of motion (ROM) AND not affecting ADL	 Tightness of arms or legs OR joint contractures, erythema thought due to fasciitis, moderated decrease ROM AND mild to moderate limitation of ADL	 Contractures WITH significant decrease of ROM AND significant limitation of ADL (unable to tie shoes, button shirts, dress self, etc.)
GENITAL TRACT	 No symptoms	 Symptomatic with mild signs on exam AND no effect on coitus and minimal discomfort with gynecologic exam	 Symptomatic with moderate signs on exam AND with mild dyspareunia or discomfort with gynecologic exam	 Symptomatic WITH advanced signs (stricture, labial agglutination or severe ulceration) AND severe pain with coitus or inability to insert vaginal speculum

Other indicators, clinical manifestations or complications related to chronic GVHD.

- Check all that apply
- Assign a score to its severity (0-#) based on its functional impact where applicable
 - none = 0
 - mild = 1
 - moderate = 2
 - severe = 3

Esophageal stricture/web _____ Pericardial Effusion _____ Pleural Effusion(s) _____
 Ascites (serositis) _____ Nephrotic syndrome _____ Peripheral Neuropathy _____
 Myasthenia Gravis _____ Cardiomyopathy _____ Eosinophilia > 500ul _____
 Polymyositis _____ Cardiac conduction defects _____ Coronary artery involvement _____
 Platelets < 100,000/ul _____ Progressive onset _____
 Others: (specify) _____

CHRONIC GVHD GRADING

MILD: involves only 1 or 2 organs or sites (except the lung), with no clinically significant functional impairment (maximum of score 1 in all affected organs or sites).

MODERATE: involves: (1) at least 1 organ or site with clinically significant but no major disability (maximum score of 2 in any affected organ or site) or (2) 3 or more organs or sites with no clinically significant functional impairment (maximum score of 1 in all affected organs or sites). Or a lung score of 1 will also be considered moderate chronic GVHD.

SEVERE: indicates major disability caused by chronic GVHD (score of 3 in any organ or site). Or a lung score of 2 or greater will also be considered severe chronic GVHD.

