11.1.5 Study Assessments

Engraftment

Neutrophil engraftment will be measured by the number of days to reach a neutrophil count of greater than or equal 500/ul for three consecutive laboratory values obtained on different day. The day of engraftment will be the first day of the three consecutive laboratory values

Platelet engraftment will be measured by the number of days to reach a platelet count of greater than or equal 20,000/ul for three consecutive laboratory values obtained on different days independent of platelet transfusions the prior 7 days. The day of engraftment will be the first day of the three consecutive laboratory values.

Acute Graft-Versus-Host Disease

Acute graft-versus-host disease will be monitored daily and will be documented 1X / week from day +7 while patient is hospitalized for transplant. After discharge from hospital, Acute GVHD will be monitored and documented at a minimum of every 21 days till day +100 (or more if clinically indicated). Acute graft-versus-host disease will be graded according to the table shown in Appendix 1. Skin, gastrointestinal, and/or liver biopsies will be obtained, when appropriate, to facilitate the diagnosis. The type and duration of immunosuppressive treatment given for aGVHD will be recorded.

Chronic Graft-Versus-Host Disease

After day 100, patients will be assessed at least every 3 months (+/- 14 days) for cGVHD. cGVHD will be graded as mild, moderate, or severe based on the National Institutes of Health Consensus Development Project according to the table shown in Appendix II. The type and duration of immunosuppressive treatment given for cGVHD will be recorded.

Mucositis

Mucositis will be graded 3 times per week (Mon-Wed-Fri) by the mid-level provider or transplant physician from day 0 until day +28 or day of discharge (whichever occurs first) according to the WHO grading scale shown in Appendix III.

Total Parenteral Nutrition (TPN)

Start and stop dates of TPN will be recorded.

IV Pain Medications

Start and stop dates for the need for continuous IV infusion of narcotics for severe mucositis pain in the form of intravenous infusion or patient controlled analgesia (PCA) will be recorded.

Length of Hospitalization

Length of hospitalization will be measured from date of transplant to date of discharge.

Organ Toxicity

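### The score 3 lung cell in the chronic GVHD table repeats the score 2 lung-function range, so the worst lung function has no functional criterion and can, in a narrow case, be graded below severe

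*Combined protocol and SAP*

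**What the plan says.** Chronic GVHD incidence and severity is a secondary objective (section 2.2) and is listed for comparison between the arms in section 12.4. Section 11.1.5 states that "cGVHD will be graded as mild, moderate, or severe", and refers the assessor to the table in Appendix II, which is headed as using the NIH consensus criteria.

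Each cell in the Lungs row of that table holds a symptom line and a lung-function line. The function line is "FEV1 > 80% OR LFS =2" for score 0 and "FEV1 60-79% OR LFS 3-5" for score 1. The score 2 cell pairs "Moderate symptoms (SOB after walking on flat ground") with "FEV1 40-59% OR LFS 6-9". The score 3 cell pairs "Severe symptoms (SOB at rest; requiring O2") with the same function line.

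The grading rules at the end of Appendix II give the lung special weight. For the moderate grade they add: "Or a lung score of 1 will also be considered moderate chronic GVHD". For the severe grade they add: "Or a lung score of 2 or greater will also be considered severe chronic GVHD". A score of 3 in any organ is also severe.

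**The concern.** The function ranges step down from score 0 to score 2 and then stop. The last cell repeats the one before it where the sequence should continue. One range therefore belongs to two scores, and the worst range belongs to none.

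This matters because the lung score can set the overall grade on its own. If the worst lung function has no functional criterion, a patient with very poor function but few symptoms could receive a lower grade than a patient with better function. That would put the severity scale out of order in a comparison the protocol intends to make. Assessors who notice the slip may supply the missing range themselves, and others may not. The available text describes no blinded assessment of chronic GVHD, so grading that depends on individual judgement is best avoided.

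**Working it through.** The plan gives no figure to reproduce here. No sample size, power or significance level depends on this table. The check is one of coverage, followed by what the grading rules do with the result.

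**Step 1. Coverage of the function scale (Appendix II, Lungs row).**

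| Score | Function line as printed | Overall grade the lung score forces |
|---|---|---|
| 0 | "FEV1 > 80% OR LFS =2" | none |
| 1 | "FEV1 60-79% OR LFS 3-5" | at least moderate |
| 2 | "FEV1 40-59% OR LFS 6-9" | severe |
| 3 | "FEV1 40-59% OR LFS 6-9" | severe |

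- FEV1 40-59% and LFS 6-9 appear twice, under scores 2 and 3.
- FEV1 below 40% and LFS above 9 appear nowhere in the table, and no other section supplies them.

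**Step 2. Effect of the overlap.** A patient with FEV1 of 50% has a lung score of 2 or 3. Both are severe under the rule quoted above. The overall grade is the same either way, and section 11.1.5 uses only the three overall grades. The overlap moves no patient between grades.

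**Step 3. Effect of the gap.** A patient with FEV1 of, say, 35% matches no function line, so only the symptom line can give a score:

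| Symptoms | Lung score from symptoms | Overall grade |
|---|---|---|
| Breathless at rest, needing oxygen | 3 | severe |
| Breathless walking on the flat | 2 | severe |
| Breathless climbing one flight of stairs | 1 | moderate, unless another organ scores 3 |
| None | 0 | set by the other organs; below severe unless one scores 3 |

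Only the last two rows can give a grade below severe. Three conditions must hold together: function in the missing range, symptoms mild or absent, and no other organ at score 3.

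**Step 4. Is the order reversed?** Take two patients with mild breathlessness and no other organ at score 3, one with FEV1 of 50% and one with 35%. Appendix II does not say how to combine a symptom line and a function line that disagree. If the higher line decides, the first scores at least 2 (severe) and the second scores 1 (moderate), so the worse function gets the lower grade. If symptoms alone decided, both would score 1 and nothing would be reversed, but the function lines would then serve no purpose.

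**Step 5. Size.** Sections 3.1 and 3.2 plan 50 patients per group. With the whole arm as denominator, k affected patients shift the proportion with severe chronic GVHD by k/50. The count k is an assumption, because the documents give no rate of lung involvement:

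- k = 0: 0 percentage points
- k = 1: 1/50 = 2 percentage points
- k = 2: 2/50 = 4 percentage points

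**The case against.** The strongest reply is that the slip is obvious and does little harm. Appendix II names the NIH consensus criteria and section 11.1.5 bases the grading on them, so an assessor has a standard to consult. The descending sequence also shows where the table went wrong. Most patients with very poor lung function will have symptoms, and moderate or severe symptoms already lead to a severe grade. Exposure is limited too. The table in section 11.1.4 schedules lung-function tests before the study, at day 100 and then as needed, in patients over 6 years, while chronic GVHD monitoring starts after day 100. Section 14 plans cumulative incidence and the Pepe-Mori test for chronic GVHD and specifies no test by severity grade.

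Most of this stands, and it limits the impact. It does not remove the defect. Section 11.1.5 sends the assessor to this table, and naming a parent standard does not say which text governs when the table departs from it. Section 12.4 still lists severity for comparison.

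A PDF reading fault cannot be fully excluded. It is unlikely, because the two cells have different symptom text and the neighbouring cells are intact. A look at the source page settles it.

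A reader might infer that every patient with FEV1 of 40-59% is at risk of misgrading. The documents do not support that: scores 2 and 3 both give severe. A reader might also infer that patients below 40% cannot be scored at all. They can, on symptoms.

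**Conclusion.** The point holds in a limited form. As printed, the lung-function scale has a duplicated range and no entry for the worst function. The duplication affects only the organ score. The gap can lower an overall grade, and reverse the order of two patients, only under the three conditions in the working. The reversal also assumes a literal reading in which the higher of the two lines decides the score.

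Each affected patient is worth 2 percentage points of severe chronic GVHD in an arm of 50. The number affected is unknown and may be zero. A reader might infer a shift of a few points, or a bias towards one arm. The documents give no basis for either, because they state no expected rate of lung disease and nothing that would make the gap fall more heavily on one group.

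The defect touches one secondary endpoint, chronic GVHD severity. No primary objective, sample size or power statement is affected. It should be corrected because the table is the operative grading instrument and the repair is small.

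**What to change.** 1. Check the source page of Appendix II to confirm that the repeated line is in the plan itself.
2. If it is, reconcile the score 2 and score 3 lung-function lines with each other and with the NIH consensus criteria the appendix says it uses. The score 3 line should continue the table's own sequence beyond the score 2 range, and the four lines should cover the whole scale without overlap. The documents do not state the intended score 3 range, so it has to be taken from those criteria.
3. Carry the correction into the case report form.
4. If any patient was graded using the faulty cell, re-score that patient from the recorded lung function and symptoms. The documents do not show whether any were.

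The cost is one correction to an appendix and its form, plus a re-score if step 4 applies. No additional patients or assessments are needed.

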APPENDIX III

WORLD HEALTH ORGANIZATION (WHO) MUCOSITIS GRADING SCALE

Grade 0	Grade 1	Grade 2	Grade 3	Grade 4
No mucositis	Soreness +/- Erythema	Erythema, ulcers; ability to eat solids	Ulcers, requires liquid diet	Alimentation not possible.

The following additional guidelines may be used in the assessment of oral mucositis

- **Grade 1** may include buccal mucosal scalloping with or without erythema. No ulcers. Patient can swallow a solid diet.
- **Grade 2** may include ulcers with or without erythema. Patient can swallow a solid diet.
- **Grade 3** may include ulcers with or without (extensive) erythema. Patient is able to swallow a liquid, but not solid diet.
- **Grade 4** refers to mucositis to the extent that alimentation is not possible. If total parenteral nutrition was started for reasons other than mucositis, a determination of the subject's ability to swallow must be made using the above criteria.

APPENDIX IV

TBI ADMINISTRATION

Patients may be treated either in the AP/PA position and/or in the right and left lateral position. Compensators or blocks may be used to compensate for the thinner parts of the anatomy (neck, head, lower legs, and feet).

Total dose will be 1200-1320 cGy in 6-8 fractions over 3-4 days with at least six hours between fractions depending on institutional guidelines. Dose will be prescribed at the level of the umbilicus at midplane.

TBI will be delivered from either a linear accelerator or cobalt source at a dose rate of between 4 and 26 cGy/minute using energies of between 1 and 25 MV.

The skin dose should be at least 90% of the prescribed dose. If a higher energy beam (> 4 MV) is used for the TBI treatments, a beam spoiler should be used to accomplish this or thermoluminescent dosimetry data submitted showing that the skin dose is at least 90% of the prescribed dose.

Testicular boosts could be used for all males with ALL (and according to institutional practices for other diseases) depending on institutional guidelines. The testicular boost recommendation is single 400 cGy fraction with either electrons prescribed to D_{max} or photons prescribed to the midplane of the scrotum. If electrons are used, the energy for the testicular boost depends on the thickness of the testicles and is chosen so that the D90 corresponds to the posterior surface of the scrotum.
